7.2. Device Malfunction or Use Errors

Device malfunctions or use errors will be recorded and evaluated for possible untoward effects on the subject. For the purposes of this study, a device malfunction is defined as a failure of the device to perform its intended function when used in accordance with the Instructions for Use (IFU). If a VeriSight device malfunction results in an adverse experience for the subject, this adverse experience should be considered an adverse device effect and recorded on the appropriate CRF. A device malfunction by itself should not be reported as ADE unless it leads to the new medical condition or worsening of pre-existing condition. If a VeriSight device malfunction occurs in this registry, the site should follow standard commercial procedures.

7.3. Reporting Requirements

Philips VeriSight catheter used in this registry for imaging during percutaneous cardiac interventional procedures is cleared for commercial use by the FDA. Therefore, the use described in this protocol constitutes a standard clinical practice use. Information related to contraindications, adverse effects, warnings and precautions are included in the device instructions for use.

Reporting for this registry will be limited to peri-procedural (at discharge or \leq 48H) ADEs, SADEs and USADEs (per the above definition) occurring while performing the index procedure with the guidance of Philips VeriSight. VeriSight may be used in the detection/monitoring of adverse events related to the procedure (i.e., post cardiac procedure thrombus recognition) during the procedure.

Adverse device effects related to the device should also be reported to the Study Medical Monitor (see below). All adverse device effects must be reported to Philips IGTD as soon as possible after first awareness of the event; every attempt must be made to report such events to Philips IGTD within 24 hours of first awareness of the event.

Study Medical Monitor contact information for adverse device effects reporting:

[name]
Medical Monitor
Philips Image Guided Therapy Devices
[contact]
Email: [contact]

The Investigator is responsible for reporting the adverse device event to the approving IRB as dictated by the guidelines defined by the IRB and, if applicable, regulatory authorities. The investigator is required to submit to the sponsor and to the reviewing IRB, a report of any unanticipated adverse device effects occurring during an investigation as soon as possible, but in

Document ID:	IGT_IGD_ICE Registry Study 2019 10745	Document title:		Classification:	Confidential
Modified:	24 APR 2021	Philips ICE Registry			
Version:	2.0	User Tool ID:	16.2.6UserTool0004		
Status:	Final	User Tool Version Date	30May2019	Page:	25

Clinical Registry Protocol IGT_IGD_ICE Registry Study_2019_10745

no event later than 10 working days after the investigator first learns of the effect. Additionally, the Investigator will report to regulatory authorities as required by national regulations.

Contact information for complaint reporting is: **[contact]**. The sites should follow standard commercial procedures for reporting device complaints. Device deficiencies are NOT to be reported as ADEs. However, if there is an ADE that results from a device deficiency, that specific event would be recorded on the appropriate case report form.

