3.2. Performance and Safety Analyses

The overall purpose of this observational multi-center registry is to report real-world performance and safety of VeriSight ultrasound guided ICE imaging in percutaneous cardiac intervention procedures when used in standard clinical practice.

Primary Analyses

The primary analyses will include the following:

- a) **Technical success** – defined by successful delivery of VeriSight to the target intracardiac position and sustained device operation during the procedure
Successful device delivery is defined as ability of the VeriSight catheter to reach the target intracardiac anatomical position. Sustained operation of VeriSight is absence of technical complications or procedural delays/ disruption.
- b) **Imaging success** – Adequate image quality as determined by the investigator using a Likert scale assessment.
- c) **Clinical success** - Adequacy of VeriSight imaging for visualization of major cardiac structures, and guiding procedural intervention, and ability to detect/ assess intra-procedural complications.
Clinical success will be measured by ability of VeriSight to adequately guide procedural intervention using the following parameters:
 - i. number of great vessels imaged, number of chambers imaged, including angle of views, axis, and modality
 - ii. assessment of key cardiac structures and sizing relevant anatomy
 - iii. verification of delivery and/or placement of interventional device (e.g. trans septal puncture devices, closure devices (LAAO, PFO, ASD, VSD), valves (e.g for TAVR), clip devices (e.g. mitral clip), annuloplasty devices (e.g. Cardioband), ablation devices (e.g cryoballoon, RF ablation catheter), leads (leads extraction), etc.),
 - iv. assessment of procedural related complication (e.g. cardiac tamponade, pericardial effusion, thrombus) will be documented for each patient based on the procedure type.

Document ID:	IGT_IGD_ICE Registry Study_2019_10745	Document title:		Classification:	Confidential
Modified:	24 APR 2021	Philips ICE Registry			
Version:	2.0	User Tool ID:	16.2.6UserTool0004	Page:	15
Status:	Final	User Tool Version Date	30May2019		

Clinical Registry Protocol IGT_IGD_ICE Registry Study_2019_10745

d) **Safety** - Device related adverse events periprocedural through discharge or 48 hours post-procedure, whichever is earlier.

Secondary Analyses

Secondary analyses will include the following:

- a) Procedural characterization when using VeriSight measured by

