4.8. Lost to Follow-Up

Follow-up in this registry is limited to discharge or ≤48 hours post-procedure, whichever is earlier. All follow-up data is expected to be collected and lost to follow-up is not anticipated in this registry.

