6.2. Schedule of Activities (SOA)

Table 1 provides an overview of registry procedures per visit.

Document ID:	IGT_IGD_ICE Registry Study_2019_10745	Document title:		Classification:	Confidential
Modified:	24 APR 2021	Philips ICE Registry			
Version:	2.0	User Tool ID:	16.2.6UserTool0004	Page:	19
Status:	Final	User Tool Version Date	30May2019		

Clinical Registry Protocol
IGT_IGD_ICE Registry Study_2019_10745

Table 1. Overview of registry procedure			
Procedures	Screening*	Index procedure	Post-Procedure (at discharge or 48hrs)
Assessment of eligibility	X		
Informed consent	X		
Record demographics	X		
Medical History and Physical (H&P)	X		
Record any baseline diagnostic imaging		X	
ICE imaging with VeriSight		X	
Image grading		X	
Procedural workflow and details		X	
Adverse device effects related to VeriSight		X	X
Registry exit			X
Usability assessment	Aggregate input		
Physical attributes of catheter	After 1 st patient enrolled	After 10 th patient enrolled	After last patient enrolled
Physician and staff survey	After 1 st patient enrolled	After 10 th patient enrolled	After last patient enrolled

*up to 30 days prior to index

Below are the brief study procedure steps.

- Subjects are evaluated for eligibility based on the inclusion and exclusion criteria
- Record demographics of subjects: age, gender, height, weight, ethnicity/race (if applicable)
- Record relevant medical and surgical histories
- The subjects will be imaged using the VeriSight device according to the routine workflows
- Relevant imaging for each procedural steps will be recorded.
- The Investigator will grade the imaging recorded
- The corresponding clinical information and information about the use of device and system, including device deficiencies and safety-related adverse device effects related to VeriSight, will be recorded by the Investigator in the CRF
- The registry examinations including all collected de-identified images will be transferred to Philips

Document ID:	IGT_IGD_ICE Registry Study_2019_10745	Document title:		Classification:	Confidential
Modified:	24 APR 2021	Philips ICE Registry			
Version:	2.0	User Tool ID:	16.2.6UserTool0004	Page:	20
Status:	Final	User Tool Version Date	30May2019		

Clinical Registry Protocol
IGT_IGD_ICE Registry Study_2019_10745

- After the completion of the procedure, subject are dismissed from the registry after monitoring for post-procedure adverse device effects either at discharge or ≤48 hrs post-procedure, whichever is sooner.

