6.5. Post-procedure

Patients will be followed up until discharge or until ≤48 hours post procedure whichever is earlier. Adverse device effects related with the use of the VeriSight device will be captured in the case report form during this visit as defined in **Section 7.0**.

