7.7. Time Period and Frequency for Event Assessment and Follow-Up

Only ADEs will be collected starting from the time the subject is enrolled until the time of discharge which is less than or equal to 48 hours post procedure. Events will be followed until resolution if possible.

Events will be reported via the electronic case report form and submitted to the Sponsor.

Information to be collected includes event description, time of onset, clinician's assessment of severity, relationship to study device (assessed only by those with the training and authority to make a diagnosis), and time of resolution/stabilization of the event.

Any medical condition that is present at the time that the subject is screened will be considered as baseline and not reported as an AE. However, if the study subject's condition deteriorates at any time during the study due to the use of the study device, it will be recorded as an ADE.

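### Protocol 7.3 contradicts itself on which device-related events are reportable, and its narrower clause falls short of the primary safety endpoint

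*Protocol*

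**What the plan says.** The primary safety analysis in Protocol 3.2 is "Device related adverse events periprocedural through discharge or 48 hours post-procedure, whichever is earlier". SAP 5.4 defines the safety variable over the same window.

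Protocol 7.3 then sets the scope of reporting in one sentence. It opens with "Reporting for this registry will be limited to peri-procedural", adds a bracket that extends the period to discharge or at most 48 hours, names ADEs, SADEs and USADEs, and closes by confining these to events "occurring while performing the index procedure with the guidance of Philips VeriSight".

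Other sections direct collection after the procedure. Section 6.5, on the post-procedure visit, says "Adverse device effects related with the use of the VeriSight device will be captured in the case report form during this visit". The steps under Table 1 in Section 6.2 release a subject only after "monitoring for post-procedure adverse device effects either at discharge" or by 48 hours. Section 7.7 says "Only ADEs will be collected starting from the time the subject is enrolled until the time of discharge".

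Follow-up length differs between subjects by design. Section 4.8 states: "Follow-up in this registry is limited to discharge or ≤48 hours post-procedure, whichever is earlier". SAP 8.3 repeats the follow-up rule, and SAP 8.8 plans counts and percentages of events and of subjects with events. Neither mentions a summary of time observed.

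**The concern.** Section 7.3 is where a site looks to decide what must be reported, and its wording is exclusionary. An event cannot be confined to the time when the procedure is being performed and also accrue until discharge or 48 hours. A coordinator who gives weight to the closing clause would leave out a device-related event that starts in the recovery area or on the ward, although the primary endpoint counts it.

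The result matters beyond description. SAP 4.1 says that the analysis at 100 subjects serves a CE mark application, Protocol 2.3 foresees regulatory filings outside the US, and Protocol 9.5 plans no safety committee that might notice a gap. If device-related events are few, losing even one or two changes the picture.

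**Working it through.** The documents give no device event rate, precision target or derived sample size for safety, so there is no figure of the plan to reproduce. The check is a comparison of wording, followed by an illustration.

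**Step 1. The windows side by side.**

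| Place | Window for device-related events |
|---|---|
| Protocol 3.2 (d); SAP 3.1 (d) and 5.4 | Periprocedural to the earlier of discharge and 48 h |
| Protocol 6.2, Table 1 and steps | Index procedure and post-procedure columns both marked |
| Protocol 6.5 | Captured at the post-procedure visit |
| Protocol 7.1, definition of ADE | No limit to the procedure |
| Protocol 7.3, bracket | To discharge or at most 48 h |
| Protocol 7.3, closing clause | During the index procedure only |
| Protocol 7.7 | Enrollment to discharge, taken to be within 48 h |

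Only the closing clause of 7.3 is narrower than the endpoint.

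**Step 2. Section 7.7 against 3.2.** Section 7.7 collects "until the time of discharge which is less than or equal to 48 hours post procedure". For a subject discharged within 48 hours this agrees with 3.2. For a subject who stays longer, 3.2 stops at 48 hours, while 7.7 assumes that the case does not arise. So 7.3 should not refer to 7.7 until 7.7 is aligned.

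**Step 3. What the narrow clause would cost if every site applied it.** All inputs except n are assumptions: a true event rate p = 2% over the endpoint window, and a share s of events that start after the procedure. The sample sizes are 100 (interim) and 200 (maximum).

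- Expected count recorded = n × p × (1 − s)
- Chance of at least one event = 1 − [1 − p(1 − s)]^n, treating each subject as having at most one event

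| n | s | Expected count | Chance of at least one |
|---|---|---|---|
| 200 | 0 | 4.0 | 98.2% |
| 200 | 25% | 3.0 | 95.1% |
| 200 | 50% | 2.0 | 86.6% |
| 200 | 75% | 1.0 | 63.3% |
| 100 | 0 | 2.0 | 86.7% |
| 100 | 25% | 1.5 | 77.9% |
| 100 | 50% | 1.0 | 63.4% |
| 100 | 75% | 0.5 | 39.4% |

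Example: 200 × 0.02 × (1 − 0.50) = 2.0, and 1 − 0.99^200 = 86.6%.

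With zero events, the exact two-sided 95% upper limit is 1 − 0.025^(1/n), which is 3.62% at n = 100 and 1.83% at n = 200. Under the narrow clause that limit would cover intra-procedural events only. The rows with s = 0 also show the result if sites follow 6.2, 6.5 and 7.7: no loss.

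**The case against.** The strongest reply is that a site would have to overlook a good deal to lose events. The bracket in the same sentence points to discharge or 48 hours. The next paragraph of 7.3 requires all adverse device effects to be reported to the sponsor, with no limit to the procedure. Table 1 marks them in the post-procedure column, 6.5 puts them on the case report form, and 7.7 is the section headed as governing the time period. This stands in large part. A reader might infer that 7.3 plainly restricts reporting to the procedure and is the controlling rule. The documents do not support that: the sentence is self-contradictory, and under-counting arises only where its last clause is followed over the rest.

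A reader might also infer that follow-up of varying length biases the safety result downwards. It does not. Ending at the earlier of discharge and 48 hours is the endpoint's own definition, and the plan does not present the result as a rate over a full 48 hours. Varying follow-up limits interpretation, and comparison across procedure types if SAP 8.9 is used for safety.

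The SAP's silence on observed time carries limited weight too. SAP 8.8 lists several summaries, SAP 12 places the tables in a separate document, and the eCRF is not available here, so it cannot be confirmed that a discharge time or such a row is absent from those.

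What does not fall away is the clause itself: it is in the protocol, it conflicts with the primary endpoint, and no other section gives it a purpose.

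**Conclusion.** The point holds as an internal contradiction. The closing clause of the reporting sentence in Protocol 7.3 conflicts with the bracket before it, with the primary safety endpoint in Protocol 3.2 and SAP 5.4, and with the collection rules in 6.2, 6.5 and 7.7. Followed literally, it removes post-procedure device-related events from a primary analysis.

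The size of any loss cannot be derived from the documents. It ranges from nothing, if sites follow the other sections, to the full share of events that start after the procedure, if every site follows the clause. The counts in the working rest on an assumed 2% rate and assumed shares of 25% to 75%; they are not estimates for this device. The 14.8% complication rate cited in Protocol 2.2 does not help, because it is an overall procedure-related rate in 27 patients having appendage closure and not a device-related rate for an ICE catheter.

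The correction should be made because it is simple and the endpoint is primary. The absence of a planned summary of observed time is a lesser matter of interpretation.

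**What to change.** - **Protocol 7.3:** delete "occurring while performing the index procedure with the guidance of Philips VeriSight" and refer to the window in Section 3.2, that is, to the earlier of discharge and 48 hours.
- **Protocol 7.7:** state the same window as 3.2, so that a stay beyond 48 hours is covered and not assumed away.
- **SAP 8.8 (minor):** summarise hours observed per subject from the end of the procedure, for example median and range. State for each event whether it began during or after the procedure, using the onset times that 7.7 already collects. If the eCRF lacks a discharge date and time, add that field.
- **Do not** report event rates stratified by hours observed. A complication can prolong the stay, so events would gather in the longer strata and mislead.

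The cost is one deleted clause, one reworded sentence, a row or two in the safety table and perhaps one data field, together with the IRB review that the protocol requires for any amendment. No visit, contact or clinical procedure changes.

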7.4. Severity of Event

The following guidelines will be used to assess event severity:

- **Mild** – Events require minimal or no treatment and do not interfere with the subjects daily activities.
- **Moderate** – Events result in a low level of inconvenience or concern with the therapeutic measures. Moderate events may cause some interference with functioning.
- **Severe** – Events interrupt a subject's usual daily activity and may require systemic drug therapy or other treatment. Severe events are usually potentially life-threatening or incapacitating. Of note, the term "severe" does not necessarily equate to "serious".)

7.5. Relationship to Study Device

Relationship to registry device administration will be determined as follows:

- Possible Relationship: An AE that follows a reasonable temporal sequence with use of the VeriSight device and follows a known response pattern to the study treatment but could have been produced by the subject's clinical state or by other therapies.
- Probable Relationship: An AE that follows a reasonable temporal sequence with use of the VeriSight device; follows a known response pattern to the study treatment; and cannot be reasonably explained by the known characteristics of the subject's clinical state or by other therapies.
- Definite Relationship: An AE that follows a plausible temporal sequence with use of the VeriSight device and follows a known response pattern to the study treatment. The reaction cannot be reasonably explained by the known characteristics of the subject's clinical state or other modes of therapy administered to the subject.
- Unknown/Impossible to Determine: Given the information available, sequence and timing of events, it is unknown or impossible to determine the relationship of the AE with the VeriSight device.

7.6. Expectedness

The Principal Investigator will be responsible for determining whether an adverse device event is expected or unexpected. An ADE will be considered unexpected if the nature, severity, or frequency of the event is not consistent with the risk information previously described for the device in this registry. Please refer to the instructions for use for a listing of adverse effects.

Document ID:	IGT_IGD_ICE Registry Study 2019 10745	Document title:		Classification:	Confidential
Modified:	24 APR 2021	Philips ICE Registry			
Version:	2.0	User Tool ID:	16.2.6UserTool0004	Page:	26
Status:	Final	User Tool Version Date	30May2019		

7.7. Time Period and Frequency for Event Assessment and Follow-Up

Only ADEs will be collected starting from the time the subject is enrolled until the time of discharge which is less than or equal to 48 hours post procedure. Events will be followed until resolution if possible.

Events will be reported via the electronic case report form and submitted to the Sponsor.

Information to be collected includes event description, time of onset, clinician's assessment of severity, relationship to study device (assessed only by those with the training and authority to make a diagnosis), and time of resolution/stabilization of the event.

Any medical condition that is present at the time that the subject is screened will be considered as baseline and not reported as an AE. However, if the study subject's condition deteriorates at any time during the study due to the use of the study device, it will be recorded as an ADE.

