ICE can be used in AF ablation procedures to guide transseptal puncture. ICE imaging can also be used in the following procedural steps, including (1) characterization of pulmonary vein anatomy (number of veins, diameter, anatomic variants), (2) transseptal catheterization, (3) catheter positioning and contact monitoring, (4) assessment of lesion formation, (5) prevention and early detection of procedural complications such as pericardial effusion or thrombus formation, (6) assessment of pulmonary veins physiology/flow before and after ablation, and (7) location of the esophagus in relationship to the pulmonary vein ostium^{25, 26}. ICE is useful to assist ablation of the cavotricuspid isthmus (CTI) in patients with typical atrial flutter. In a randomized trial that included 102 patients with typical flutter, ICE-guided ablation of the CTI significantly shortened the procedure time radiation exposure, and time spent for ablation in comparison with fluoroscopy-only procedures. About 13% of the patients from the fluoroscopy-only group crossed over to ICE guidance because of failure to achieve CTI block and were all treated successfully²⁷.

ICE has an invaluable role in the mapping and ablation of ventricular arrhythmias. It provides real-time visualization of the ablation catheter in relation to a particular anatomic structure, allowing for continuous assessment of catheter–tissue contact. This is key for effective energy delivery to the targeted structure of interest, possibly increasing effectiveness and limiting collateral damage. Lesion formation is typically visualized in ventricular tissue as the development of increased echogenicity during ablation²⁸. Saksena et al. studied the role of ViewFlex ICE catheter in comparison to TEE in imaging of left atrium and interatrial septal during atrial fibrillation. ICE and TEE showed concordance for LAA, IAS and SEC imaging but not for LA and LAA thrombus detection where ICE imaging was less sensitive compared to TEE for LAA thrombus identification. There were no adverse events or complications reported for ICE or TEE²⁹.

Transvenous Lead Extraction

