2.4. Risk/Benefit Assessment

This will be an open-label all-comers registry. The design of the protocol is observational and there are no interventions as part of the registry. All interventions such as procedures occurring during this protocol are the standard clinical practice and their use will be directed by the investigator as part of the standard care. The Philips VeriSight ICE catheter has received 510(k) clearance from FDA allowing U.S. commercial sale. Investigators enrolling patients into the registry, will be imaged with the VeriSight catheter. Use of the product in this registry will be on label per the IFU and standard clinical practice. Patients will not be placed at additional clinical risk by participating in this registry. Although there are no added risks due to standard of care, the benefit at large will involve a better understanding of the safety profile for the ICE catheter tech within the respective intervention. Any complications associated with the VeriSight catheter and those related to the cardiac intervention procedures will be collected and reported.

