6.4. Index Procedure

Subjects enrolled in the registry will undergo imaging using the VeriSight catheter at the time of the index procedure. This visit will consist of the following procedures.

The indication for ICE imaging and the types of procedures that utilized VeriSight will be documented. Patient management and treatment decisions are at the discretion of the care team per routine standard clinical practice. The model of VeriSight and the venous access approach are to be per the investigator's discretion. Confirmation of the delivery of the VeriSight catheter to reach the target intracardiac anatomical position including the number of attempts depending on the procedure type will be recorded. The sustained operation of the catheter will be monitored throughout the case and recorded as part of the device technical complications including device malfunction/ deficiency and any additional procedural delays/ disruption when using VeriSight for various procedures.

Clinical data on the imaging views obtained during the procedure will be obtained. The angle of the views (0, 45, 90, 135 sweep) including axis, and the use of xPlane, iRotate, 2D or 3D, TrueVue, MultiVue modalities are left to the investigator's discretion. The anatomical landmarks for image quality assessment depend on the procedure type. Image acquisitions of cardiac structures with VeriSight shall be recorded depending on the procedure type.

The sequence of imaging for each procedure type are according to physician workflow preference. The method and access to the left atrium including transseptal puncture depending on the procedure type are to be per the investigator's discretion. For each procedure labeled screenshots and respective measurements will be documented for key procedural steps. The number of great vessels and chambers imaged will be documented. Sizing relevant anatomy for intervention or device placement and visualization, guidance and verification for delivery and/or placement of interventional device will also be noted in the case report form. Imaging with VeriSight for visualization and evaluation of intra-procedural complications and hemodynamic monitoring will be captured. Images obtained from different procedure types will be reviewed by the participating investigators at regular intervals as part of ongoing development of standard of care workflow with VeriSight ICE imaging.

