3.1 Primary Objectives

The primary objectives will include the following:

- a) **Technical success** – defined by successful delivery of VeriSight to the target intracardiac position and sustained device operation during the procedure

Successful device delivery is defined as ability of the VeriSight catheter to reach the target intracardiac anatomical position. Sustained operation of VeriSight is absence of technical complications or procedural delays/ disruption.
- b) **Imaging success** – Adequate image quality as determined by the investigator using a Likert scale assessment.

Document ID:	ICE VeriSight Registry SAP	Document title:		Classification:	For internal use
		Statistical Analysis Plan			
Modified:	02SEP2022			Author:	[name]
Version:	1.0	User Tool ID:	16.2.6UserTool0025	Approver:	[name]
Status:	Final	User Tool Version Date:	29Oct2019	Page:	5 of 16

Statistical Analysis Plan

c) **Clinical success** - Adequacy of VeriSight imaging for visualization of major cardiac structures, and guiding procedural intervention, and ability to detect/ assess intra-procedural complications.

Clinical success will be measured by ability of VeriSight to adequately guide procedural intervention using the following parameters:

- i. number of great vessels imaged, number of chambers imaged, including angle of views, axis, and modality
- ii. assessment of key cardiac structures and sizing relevant anatomy
- iii. verification of delivery and/or placement of interventional device (e.g. transeptal puncture devices, closure devices, Left Atrial Appendage Occlusion (LAAO), Patent Foramen Ovale (PFO), Atrial Septal Defect (ASD), Ventricular Septal Defect (VSD), valves (e.g for TAVR), clip devices (e.g. MitraClip), annuloplasty devices (e.g. Cardioband), ablation devices (e.g cryoballoon, RF ablation catheter), leads (leads extraction), etc.)
- iv. assessment of procedural related complication (e.g. cardiac tamponade, pericardial effusion, thrombus) will be documented for each patient based on the procedure type.

d) **Safety** - Device related adverse events periprocedural through discharge or 48 hours post-procedure, whichever is earlier.

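### The documents disagree on whether complications unrelated to the device are collected, and none requires recording a procedural complication that VeriSight did not show, which biases the detection element of clinical success upward

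*Protocol*

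**What the plan says.** **The primary element.** Protocol 3.2 c and SAP 3.1 c and 5.3.1 c define clinical success as "Adequacy of VeriSight imaging for visualization of major cardiac structures, and guiding procedural intervention, and ability to detect/ assess intra-procedural complications". Item iv adds that "assessment of procedural related complication (e.g. cardiac tamponade, pericardial effusion, thrombus) will be documented for each patient based on the procedure type".

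**Text limiting collection to device effects.**
- Protocol 7.7: "Only ADEs will be collected starting from the time the subject is enrolled until the time of discharge".
- Protocol 7.3: "Reporting for this registry will be limited to peri-procedural" ADEs, SADEs and USADEs.
- Protocol Table 1: the only safety row is for adverse device effects of VeriSight, at the index procedure and post-procedure.
- Protocol 6.4, safety evaluation: peri-procedural complications attributed to VeriSight.
- Protocol 6.5: adverse device effects of VeriSight.

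**Text going wider.**
- Protocol 2.4: "Any complications associated with the VeriSight catheter and those related to the cardiac intervention procedures will be collected and reported".
- Protocol 3.2 c iv and SAP 5.3.1 c: complication assessment for each patient, without a device-related restriction.
- SAP 8.8: counts of subjects with any AE, any SAE, and any procedure- or device-related event.

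**Capture during the procedure.** Protocol 6.4 says that "Imaging with VeriSight for visualization and evaluation of intra-procedural complications and hemodynamic monitoring will be captured". It also collects other standard-of-care imaging when it is used alongside VeriSight or as a conversion.

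**The concern.** To judge how well an imaging catheter detects complications, one has to know which complications occurred, including those it did not show. The examples in item iv (tamponade, effusion, thrombus) will mostly arise from the intervention rather than from the imaging catheter, so most will not be adverse device effects. Under the rule in section 7, an effusion caused by a septal puncture and first seen on TTE before discharge has no required place in the event data.

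Two things are at stake. The detection element of a primary analysis could rest mainly on complications that VeriSight itself showed. The SAP 8.8 tables could also carry all-AE and procedure-related headings over data collected under a narrower rule. Sites that follow section 2.4 and sites that follow section 7 would contribute different data to a pooled analysis. The results are meant for publications and for regulatory filings outside the US (protocol 2.3), and the analysis at 100 subjects is meant for a CE mark application (SAP 4.1).

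**Working it through.** The plan gives no detection rate and no precision target, so there is no figure of its own to reproduce. The check is a comparison of the sections, the direction of the bias, and an illustration of scale.

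**1. Is a complication that is not device-related collected?**

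| Yes, or presumed | No |
|---|---|
| Protocol 2.4 | Protocol Table 1 |
| Protocol 3.2 c iv; SAP 5.3.1 c | Protocol 6.4 safety evaluation; 6.5 |
| SAP 8.8 | Protocol 7.3; 7.7 |

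The left column has no matching visit procedure in the schedule of activities. The right column is the text a site works from when it completes the safety forms. SAP 5.4, which defines the safety variable, is device-related only, so the SAP also differs internally from its own 8.8.

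**2. Is a complication missed by VeriSight required to be recorded?** No section requires it. Protocol 6.4 captures VeriSight imaging of complications. It collects other imaging when used, but does not ask whether that imaging showed something VeriSight had not. No section names a source of ascertainment, a denominator for detection, or the effect of a miss on a subject's clinical success.

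**3. Direction of bias.** Let m complications occur during procedures and let VeriSight show d of them, all recorded. Let q be the fraction of the m − d misses that reach the data. The observed ratio is

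d / [d + q(m − d)]

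This equals d/m when q = 1 and exceeds d/m for any q below 1 (when d > 0 and some are missed). The device-only rule lowers q for complications of the intervention. The bias is therefore upward. Its size depends on q and on d/m, and the documents give neither.

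**4. Scale (assumption).** Protocol 2.2 quotes major peri-procedural complication rates of 1.8% (ICE group) and 4.7% (TEE group) from one left atrial appendage occlusion study. They are applied here to a mixed population for illustration only.
- At 200 patients: 200 × 0.018 = 3.6 and 200 × 0.047 = 9.4, so about 4 to 9 events.
- At the interim of 100: 1.8 to 4.7 events. At 1.8% the chance of none is (1 − 0.018)^100 = 16%.

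**5. Precision with complete recording.** When all m of m complications are shown, the Clopper-Pearson two-sided 95% lower limit is 0.025^(1/m).
- m = 4: 0.025^(1/4) = 39.8%.
- m = 9: 0.025^(1/9) = 66.4%.

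**6. Effect on the per-subject proportion.** SAP 6 measures endpoints per subject and 8.7.1 reports clinical success as a proportion. Two missed complications in two different subjects would move it by at most 2/200 = 1 percentage point. The bias matters for a statement about detection far more than for the headline clinical success figure.

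**The case against.** The strongest reply is that 7.7 belongs to the safety-reporting section and does not govern the procedural case report form, where the clinical success data are recorded. On that reading, item iv and 2.4 already cover procedure-related complications, the other imaging collected under 6.4 could reveal a miss, and SAP 8.8 shows that wider data are expected. The eCRF is not among the documents and may already hold such a field. The registry is also descriptive and tests no hypothesis.

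Much of this stands. A reader might infer that missed complications can never be counted, or that detection is complete by design. The documents do not support that: the wider sections exist, 6.4 does not say complications are captured solely through VeriSight, and no detection rate is defined that could come out at 100%.

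A reader might also infer from the background statement that "ICE imaging was less sensitive compared to TEE for LAA thrombus identification" that misses are to be expected here. That statement concerns another ICE catheter, compared with TEE for thrombus in atrial fibrillation rather than for procedural complications. Known intracardiac thrombus is an exclusion in this registry. The inference does not carry over.

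The reply leaves two points unanswered. The sections still conflict on what is collected, and places where a miss could appear are not a requirement to record it.

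**Conclusion.** The point holds as a contradiction between sections together with an incompletely specified part of a primary analysis. Under the device-only rule the detection element is biased upward by an amount that cannot be computed from the documents, and the AE, SAE and procedure-related counts in SAP 8.8 would be incomplete. The primary safety endpoint is explicitly device-related and is not affected.

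The scale of about 4 to 9 events in 200 rests on rates from a single appendage-occlusion study. Those rates cover all major complications, not only those visible on ICE during the procedure, and the registry also includes electrophysiology, valve and ASD/PFO cases. This should be corrected because it concerns a stated collection rule and a primary analysis. It does not undermine the registry as a whole.

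**What to change.** **Protocol.** Reconcile Table 1, the 6.4 safety evaluation, 6.5, 7.3 and 7.7 with 2.4, 3.2 c iv and SAP 8.8. Record on the eCRF every intra-procedural or procedure-related complication known from standard care up to discharge or 48 hours, whatever its cause. For each, record how it was first detected (VeriSight, TEE, TTE, fluoroscopy, clinical signs) and whether VeriSight showed it. No additional examinations are needed.

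**SAP 5.3.1 c and 8.7.1.**
- Report descriptively the complications shown by VeriSight over all recorded intra-procedural complications, with an exact 95% interval.
- Count a complication identified during the procedure by another source, but not shown by VeriSight, as a failure of that component for that subject.
- List complications first found after the procedure separately, since it may not be possible to tell whether they were present during imaging.

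**Unchanged.** Keep the primary safety endpoint device-related.

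**Cost.** One short eCRF section for a handful of events, plus protocol and SAP wording; the protocol change needs IRB approval. The downsides are a little more data entry and a possibly less favourable figure. The detection estimate will remain imprecise, so it should be presented with its interval and the event count.
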